6.2.1 Survey

6.2.1.1. Original Design Assumptions

Each month we will enroll 25 Veterans; roughly 20 of whom are vaccinated and 5 of whom are unvaccinated (total: 360 receiving vaccine; 90 not receiving vaccine). We will oversample recently vaccinated Veterans to ensure an adequate sample size to attempt to describe the impact of the VAI on COVID-19 vaccine acceptance after considering other factors using purposive sampling. This is primarily a descriptive aim as there is no *a priori* data to guide sample size/power calculations.

6.2.1.2 Actual Design Assumptions

We were unable to reach the target sample size of 450 and were only able to enroll 228 individuals with 224 eligible surveys: 139 (62.1%) vaccinated and 85 (38.9%) unvaccinated individuals.

7. INTERIM MONITORING

There is no planned interim monitoring for this study.

8. DATA COLLECTION AND DATA FREEZE

8.1 Aim 1

Data from Aim 1 will be obtained from the VA Corporate Data Warehouse (CDW) and supplemented with data from other VA administrative data (e.g., VA COVID-19 Shared Data Resource, Medicare data). Table 2 provides the study initiation for each site and the last day of 12-month follow-up for eligible participants. In the subsequent Project Modification, we added two additional follow-up timepoints of 15 and 18 months after study site initiation. The last follow-up for any participant will be 10/19/2023 – at which point the trial database will be closed/frozen and be considered ready for final analysis.

Table 2: Study initiation and follow-up completion by study site

Study Site	Initiation Date	Follow-up	
		Completion Date	
Little Rock, AR	02/14/2022	02/13/2023	
Fayetteville, AR	02/14/2022	02/13/2023	
Las Vegas, NV	03/08/2022	03/07/2023	
Reno, NV	03/08/2022	03/07/2023	
Palo Alto, CA	03/21/2022	03/20/2023	
Northern CA, CA	03/21/2022	03/20/2023	
Honolulu, HI	03/23/2022	03/22/2023	
Fresno, CA	03/23/2022	03/22/2023	
New Orleans, LA	04/20/2022	04/19/2023	
Houston, TX	04/20/2022	04/19/2023	

8.2 Aim 2

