5.8.a. Aim 1 Evaluation Plan. Data for Aim 1 will come from the VA Corporate Data Warehouse (CDW) and other VA databases, such as the VA COVID-19 Shared Data Resource. Outcome data will include receipt of a COVID-19 vaccination (one or more doses of Pfizer, Moderna, Johnson and Johnson, or other WHO-authorized vaccine; completed primary series with two doses of Pfizer, Moderna, one dose of Johnson and Johnson, or the specified number of doses for other WHO-authorized vaccines) and receipt of the seasonal flu vaccine (exploratory hypothesis) during the one-year trial. Covariates will include baseline demographics (e.g., age, race/ethnicity, gender, service connection), clinical and mental health diagnoses, and medications and healthcare utilization in the year prior to the start of the trial (e.g., VA and non-VA primary care visits, inpatient hospitalizations). The primary data sources for VA-administered vaccines are the ORDCOVID Vaccine tables, which are enhancements of the CDW Immunization table and is updated weekly. Immunizations performed outside VHA for which the administration fees are reimbursed by VHA will be ascertained from CDW Community Care data in the Payment Integrity Tool (PIT) files and the Integrated Veteran Care Consolidated Data Set. which replaced PIT. Immunizations for which administration fees are reimbursed by Medicare will be ascertained from the Centers for Medicare and Medicaid Services (CMS) Institutional Outpatient, Carrier, and Medicare Advantage files using the guarterly and annual updates as they become available through the VA Information Resource Center (VIREC). Aggregate data for county vaccination rates for adults older and younger than 65, by week, are available from the CDC COVID Data Tracker dataset "COVID-19 Vaccinations in the United States, by County". (See Data Analysis section below for plan to ascertain vaccination status for Veterans who receive COVID-19 vaccination outside of VA in which vaccination data is not accessible to VA researchers.)

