9.1.6 Analysis of Exploratory Outcomes

No control for multiplicity will be performed for exploratory outcomes. We will use the same methods proposed to analyze the primary and secondary outcomes to analyze receipt of a booster vaccination and flu vaccination. We will adapt methods presented by Sinclair et al. (2012) to estimate the spill-over effect of the intervention by analyzing receipt of seasonal flu vaccination. CDC guidelines on the minimum length of time between COVID-19 primary series completion and booster eligibility decreased during the study period. We will use the most recent guideline in effect during our study period, which was a minimum of 60 days from primary series completion to receipt of the first booster. In instances where a third mRNA vaccine dose was administered prior to 60-days following the second mRNA dose, that is classified as an additional primary series dose per CDC guidelines for Veterans with immunosuppression, and the date of that vaccination is defined as the date of primary series completion. Due to difficulties ascertaining which Veterans have immunosuppression, and the relatively loose guidelines for which conditions qualify, third doses have been defined empirically based on vaccination dates.

Because of evolving guidance on COVID vaccinations (products, dosing, etc.) in the context of fluctuating background COVID-19 prevalence at different VAHCS sites combined with seasonal flu vaccination in the Fall and Winter months, we expect temporal and site trends. Therefore, we plan to conduct the following exploratory analyses: (1) adjust for time-dependent variables; and (2) perform analyses stratified by time period and site.

9.2 Aim 2

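### Freezing the database on 10/19/2023 leaves the added 18-month timepoint with 0 to 67 days of record run-out, depending on site; the 12-month analyses keep at least 183 days

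*SAP*

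**What the plan says.** SAP 8.1 explains its Table 2 as follows: "Table 2 provides the study initiation for each site and the last day of 12-month follow-up for eligible participants". The ten sites start in five same-date pairs between 02/14/2022 and 04/20/2022. The table's first row, for instance, reads "Little Rock, AR 02/14/2022 02/13/2023".

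The same section reports that, in a later modification, "we added two additional follow-up timepoints of 15 and 18 months after study site initiation". It then fixes one calendar date for every site: "The last follow-up for any participant will be 10/19/2023 – at which point the trial database will be closed/frozen".

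Protocol 5.8.a describes the sources. The tables for VA-administered vaccines are "enhancements of the CDW Immunization table and is updated weekly". Outside doses that VA reimburses come from community-care payment files. Protocol 5.2.b (Aim 2) adds that some outside doses are never reported to VA or captured by it.

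The primary and secondary outcomes are analysed at 12 months (SAP 9.1.4 and 9.1.5). SAP 9.1.6 also plans, as exploratory work, to "perform analyses stratified by time period and site". Neither document, as supplied, sets a minimum interval between the end of a follow-up window and the data extraction, or a later extraction for the added timepoints.

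**The concern.** A dose counts only if its record is in the database when the database is frozen. If the freeze falls on the last day of follow-up, doses given shortly before it may not yet have arrived. With staggered starts and a single freeze date, the time allowed for arrival differs by site and by timepoint. The 18-month reading is then less complete than the 12-month reading, and the late-starting sites are less complete than the early ones.

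At stake is any statement about uptake after month 12. The further rise between 12 and 18 months could be understated, and part of the difference between sites could reflect the freeze date and not vaccination. The plan already treats timing-dependent capture as a source of bias: SAP 9.1.3 removes IZ Gateway records from the main analyses because their capture depends on when a Veteran received care. Unequal run-out is a problem of the same kind, and no rule covers it.

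**Working it through.** **Inputs.** Site start dates, 12-month end dates and the freeze date are from SAP 8.1 and Table 2. The weekly refresh is from Protocol 5.8.a. Recording delays are assumptions, because the documents give none.

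**Step 1: reproduce the plan's dates.** End of window = start + months − 1 day. With 12 months this returns all ten completion dates in Table 2. With 18 months and a start of 04/20/2022 it returns 10/19/2023, the stated last follow-up and freeze date.

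**Step 2: run-out = 10/19/2023 − end of window, in days.**

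| Sites | 12 months | 15 months | 18 months |
|---|---|---|---|
| Little Rock, Fayetteville | 248 | 159 | 67 |
| Las Vegas, Reno | 226 | 134 | 42 |
| Palo Alto, Northern CA | 213 | 121 | 29 |
| Honolulu, Fresno | 211 | 119 | 27 |
| New Orleans, Houston | 183 | 92 | 0 |

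Taking the anniversary date as the window end shifts every figure down by one day and changes nothing of substance.

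**Step 3: size of the loss.** Assume an exponential recording delay with mean m days, doses spread evenly over a window of L days, and run-out of R days. The share of the window's doses not yet recorded at the freeze is

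(m/L) × (1 − exp(−L/m)) × exp(−R/m).

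The primary outcome is receipt of at least one dose, so the natural 18-month reading is cumulative. L is 548 days for the last two sites (04/20/2022 to 10/19/2023) and 546 for the first two (02/14/2022 to 08/13/2023).

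| Mean delay m | 18 months, R = 0 | 18 months, R = 67 | 12 months, R = 183 (L = 365) |
|---|---|---|---|
| 3.5 days (roughly the weekly refresh) | 0.6% | 0.0% | 0.0% |
| 14 days | 2.6% | 0.02% | 0.0% |
| 30 days | 5.5% | 0.6% | 0.02% |
| 60 days | 10.9% | 3.6% | 0.8% |

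Example: for m = 30 and R = 0, (30/548) × (1 − exp(−548/30)) = 5.5%. With R = 67 and L = 546, the factor exp(−67/30) = 0.107 brings this to 0.6%.

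These are shares of doses. The share of Veterans whose status changes is smaller, because a late dose in someone who already has a counted dose alters nothing.

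**The case against.** The strongest reply is that no specified inference depends on month 18. SAP section 9 defines no 15- or 18-month estimand, model or test, and the primary and secondary outcomes are read at 12 months. The time-period analyses in SAP 9.1.6 answer changing vaccine guidance, COVID-19 prevalence and the flu season; they do not mention the added timepoints. This stands, and it limits the point to a supplementary timepoint.

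Three stronger readings are tempting, and the documents support none of them.

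- **Large losses.** Looking only at doses given in months 15 to 18 (L = 92, R = 0), the same formula gives 3.8%, 15%, 31% and 51% for the four mean delays. That is the wrong denominator for a cumulative at-least-one-dose outcome, and the upper figures need delays that the documents do not state.
- **Apparent fading.** A cumulative proportion cannot fall between 12 and 18 months because records arrive late. Its rise can only be understated.
- **Bias between arms.** Arms by site are not given. If each same-date pair holds one site per arm, run-out is balanced by arm. If not, it may differ. Neither can be shown.

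It can also be said that the Bayesian sensitivity analysis (SAP 9.1.4.2) allows a misclassification rate for each timepoint. It helps only in part. The rate is described by timepoint and not by site, and its lower bound comes from Medicare data for 2021–2022, which cannot reflect an October 2023 freeze. Finally, more run-out does not recover doses that VA never captures, so this concerns late records only.

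**Conclusion.** The point holds for the added timepoints. The freeze date and the staggered starts are stated, and the run-out of 0 to 67 days at 18 months follows from them exactly. Under-recording of late doses is a consequence of that rule, given a weekly refresh and payment-file sources. Its size is uncertain: about 0.6% of cumulative doses at the last two sites if only the weekly refresh matters, rising to about 11% at a mean delay of 60 days. Both figures rest on exponential delay and even dosing; if doses cluster late in the window, the loss is larger.

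The 12-month primary and secondary results are in effect untouched. Even at a 60-day mean delay, the site with the least run-out would lack about 0.8% of its 12-month doses. The point merits a correction to the SAP, but it does not threaten the trial's main conclusion.

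**What to change.** In SAP 8.1, separate the end of follow-up from the freeze. Keep 10/19/2023 as the last date on which a dose can count at New Orleans and Houston, with each other site's own 18-month date as its limit. Set the extraction and freeze for the 15- and 18-month timepoints later by a stated minimum run-out, for example 90 days: 10/19/2023 + 90 days = 01/17/2024.

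State it as a minimum. An equal 90-day run-out imposed at every timepoint would cut the 12-month run-out from 183–248 days and discard records already held. It would also need record-entry dates, which the documents do not mention. Say too which lock date governs the IZ Gateway sensitivity analysis, since a later lock admits more Veterans to it.

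If the freeze cannot move or has already been carried out, label the 18-month result as incompletely recorded at the last two sites and draw no conclusion about the trend from 12 to 18 months.

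The cost is a few sentences of SAP text, one later data pull and about three months' delay for the supplementary timepoints. The 12-month analysis need not wait.

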8.2.1. Survey Data

Aim 2 survey data were collected from 5/25/2022 to 8/7/2023.

9. ANALYSIS PLAN

This section describes the analysis of the primary, secondary, and exploratory outcomes for Aims 1 and 2. The analytic plan will be modified as necessary up to final data lock and before study unblinding. Results will be reported to clinicaltrials.gov within one year of obtaining all data necessary to analyze the primary outcome on the last patient. The trial has been registered on clinicaltrials.gov: NCT05027464. Data analysis will be performed by the unblinded statisticians. Current versions of SAS and R will be used for all analyses.

9.1 Aim 1

9.1.1 General Approach

Analyses will be based on the intent to treat principle, that is any Veteran at the start of the trial who receives VHA primary care services at a participating site within one year of the study start date (Aim 1) will be considered in the denominator of the vaccination rate regardless of whether they received the intervention. Randomization was stratified by VISN and constrained based on baseline vaccination rate; therefore, all analyses will adjust for VISN and baseline vaccination rate. Since randomization was conducted at the site level, but analyses will include individual level data, we will assess the adequacy of the randomization by comparing baseline characteristics of participants between the two groups. No statistical tests will be used to assess these comparisons. Variables will be summarized using descriptive statistics. Nominal and ordinal categorical variables will be summarized using frequencies and percentages. Continuous variables will be summarized with the following descriptive statistics: N, mean, standard deviation, median, minimum, maximum, interquartile range, and range. We will also use plots (e.g., box and whisker) to explore the distribution of the data. Both the primary and secondary outcome will be tested with an alpha of 0.05 (two-sided). All other outcomes will be considered exploratory and will not be subject to corrections for multiple testing.

9.1.2 Comparability of Baseline Characteristics

We will present baseline site and participant characteristics (mean, standard deviations, medians, and quartiles for continuous variables; frequency and percentages for categorical variables) by treatment group and use the summary statistics to assess for adequate balance of relevant confounders; no inferential statistics will be used. Given that the randomization was conducted at the site level and analyses will be conducted at the individual level, variables that appear to be different between the VAI and usual care arms will be adjusted for in sensitivity analyses. Study results will be reported according to the Consolidated Standards of Reporting Trials (CONSORT).

9.1.3 Background of Vaccination Records Ascertainment

The uncertainty in vaccine records ascertainment is pertinent to discuss prior to describing how we will analyze the primary, secondary, and exploratory outcomes with standard and sensitivity analyses. There will be Veterans who receive their COVID-19 vaccinations outside of the VA system or from venues not currently captured in VA databases (i.e., State fairs, shopping malls etc.). This could inflate our denominator of unvaccinated Veterans at the start of the trial (i.e., false negatives – Veterans are actually vaccinated). It could also decrease our numerator during the trial because we could miss Veterans who received COVID-19 vaccines during the study follow-up period at non-VA sites not captured in VA data. There are two main avenues to supplement missing vaccine information in VA records; however, both have important limitations.

First, we will supplement VA vaccination records with Medicare claims data. While the federal government paid for the vaccine product, providers were permitted to bill for the cost of administering the vaccines. Based on analyses from the VA Information Resource Center (VIReC) in 2021, linking Medicare data substantially improved ascertainment. There are a few limitations. First, due to a lag, claims data will not be available for the complete study period. For Veterans enrolled in traditional Medicare fee-for-service, which account for approximately 70% of Medicare-enrolled Veterans, we anticipate data being available through 2022 [Centers for Medicare and Medicaid Services (2021)]. For Veterans enrolled in Medicare Advantage (i.e., managed care programs), data will only be available through 2021. Second, during the early phases of vaccine rollout in 2021 when mass vaccination clinics had been common, Centers for Medicare and Medicaid Services estimated that claims were never submitted for as many as half of Medicare-age people.

Second, VHA has been developing a health information exchange with state Immunization Information Systems (IIS) in partnership with CDC to query and report Veteran immunization records. This exchange, known as the IZ Gateway, began querying state registries for 9 of the 10 study sites during July and August of 2023. Unfortunately, VHA does not plan to query state registries retrospectively for all Veterans. Instead, VHA will query individual Veterans' records when they receive VA health services. Accordingly, we anticipate differential vaccine ascertainment in which Veterans who receive care from the time the Gateway was activated in their home state until the final data lock for this study will have near-complete vaccine ascertainment; in contrast, Veterans who do not receive care during this period will have less-complete ascertainment. Vaccine records populated through the Gateway can be identified which will help us to evaluate potential biases resulting from the timing of the Gateway rollout. For the main analyses, records populated through the IZ Gateway are being removed from the analytic dataset to avoid differential bias.

Due to limitations of the IZ Gateway and Medicare data, we will utilize one or more of several methods to ascertain the missing vaccination records and its impact on our estimates. These include comparison of our rates to those published by state and federal authorities for our VISNs or comparison of our rates to those reported by national and local VA dashboards. Alternatively, to estimate population levels of underreporting, we may need to utilize survey sampling methodology and probability weighting to randomly survey Veterans with no documentation of COVID vaccination. In sum, primary analyses for Aim 1 will utilize only VA electronic health data to ascertain Veterans' vaccination status. We will also conduct sensitivity analyses that incorporate all available data sources (e.g., electronic health records; Medicare; state-level records; IZ Gateway).

9.1.4 Analysis of the Primary Outcome

To analyze the primary outcome (receipt of any COVID vaccination), we will use a multi-level model that considers the hierarchical clustering [Guo et al. (2000)] for a binary outcome and adjusts for region (VISN) and baseline vaccination rate to estimate the difference in proportion of vaccinated Veterans at 12-months between VAI and usual care. The model will also be *a priori* adjusted for the following participant level covariates: age, race/ethnicity, gender, health care utilization one year prior to the start of the trial. We will report the difference in rates between the VAI and usual care arms and 95% confidence interval.

Sensitivity Analyses

9.1.4.1 Expanding Analyses to Include Vaccination Records from Medicare/Medicaid and IZ Gateway

We plan to incorporate the vaccination records from Medicare/Medicaid and the IZ gateway and run sensitivity analyses for the primary outcome. These supportive analyses will provide variation in the estimated intervention effect related to incorporating external sources of vaccination records. On account of the IZ Gateway querying state IIS records on a prospective basis, these sensitivity analyses will focus on Veterans who have received care since the IZ Gateway was activated in their home states, which for the study sites happened during July or August of 2023. The specified statistical model is identical to that laid out in Section 9.1.4.

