9.1.5.1 Expanding Analyses to Vaccination Records from Medicare/Medicaid and IZ Gateway

We plan to incorporate the vaccination records from Medicare/Medicaid and the IZ gateway and run sensitivity analyses for the secondary outcome. The motivation and analysis model are identical to that laid out in Section 9.1.4.1. We will include Veteran records provided by these additional data sources who were not reported to have completed or initiated the primary series at randomization.

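### The Medicare and IZ Gateway sensitivity analysis changes records and population in one step, and no VA-only run in the same subset is specified to separate the two

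*SAP*

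**What the plan says.** **Reference analysis.** SAP 9.1.3 states that "primary analyses for Aim 1 will utilize only VA electronic health data" and removes Gateway records from the main analyses. SAP 9.1.1 keeps every eligible Veteran in the denominator; SAP 6.1.1.2 counts 338,718 (190,427 usual care, 148,291 intervention). SAP 9.1.4 estimates the 12-month difference in proportions with a multi-level model. It adjusts for VISN, baseline vaccination rate, age, race/ethnicity, gender and "health care utilization one year prior to the start of the trial".

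**Sensitivity analysis.** SAP 9.1.4.1 adds Medicare/Medicaid and Gateway records, keeps the model unchanged, and says that the results "will provide variation in the estimated intervention effect related to incorporating external sources of vaccination records". Because registries are queried only when a Veteran uses VA services, it adds that "these sensitivity analyses will focus on Veterans who have received care since the IZ Gateway was activated in their home states". For the secondary outcome, SAP 9.1.5.1 says: "The motivation and analysis model are identical to that laid out in Section 9.1.4.1". Protocol 5.9 has matching text for both outcomes.

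**Reason for the subset.** SAP 9.1.3 expects that Veterans seen from activation "until the final data lock for this study will have near-complete vaccine ascertainment", and that capture is poorer in the rest. It also says that Gateway records "can be identified which will help us to evaluate potential biases resulting from the timing of the Gateway rollout", but names no analysis that would do this.

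**Site coverage.** SAP 9.1.3 says the Gateway "began querying state registries for 9 of the 10 study sites during July and August of 2023". SAP 9.1.4.1 gives the same months for the study sites with no exception.

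**The concern.** A sensitivity analysis meant to show the influence of a data source should change the data source and nothing else. Here the comparison with the primary estimate changes two things: the records that define the outcome, and the Veterans who are analysed.

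The second change is not obviously neutral. Membership depends on VA care received after randomization and after the primary outcome window. Protocol 5.2.b (Aim 2) reports fewer outpatient visits among Veterans recorded as unvaccinated (5.99 against 8.23) and says that utilization is associated with vaccination.

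The primary analysis is expected to miss doses given outside VA, and 9.1.4.1 is the only analysis set out in detail that puts Medicare and Gateway records into the effect estimate. Readers will look to it to judge whether missed doses matter. If it differs from the primary result, they cannot tell which change was responsible. If it agrees, they cannot tell whether neither change mattered or the two offset each other.

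**Working it through.** The plan gives no figure for this analysis, so there is none to reproduce; the power figures in SAP Table 1 do not bear on it.

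**1. When the subset is defined.** Inputs are the 12-month completion dates in SAP Table 2 (section 8.1) and activation in July or August 2023. Site activation dates are not given, so I take 1 July and 31 August as limits.

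| 12-month window closed | Days to 1 Jul 2023 | Days to 31 Aug 2023 |
|---|---|---|
| 13 Feb 2023 | 138 | 199 |
| 7 Mar 2023 | 116 | 177 |
| 20 Mar 2023 | 103 | 164 |
| 22 Mar 2023 | 101 | 162 |
| 19 Apr 2023 | 73 | 134 |

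Entry therefore opens 73 to 199 days after the primary window closes. If the data lock is the 19 October 2023 freeze, a Veteran has between 111 days (from 1 July, inclusive) and 50 days (from 31 August) in which to enter.

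**2. Whether the utilization covariate covers this.** It describes the year ending at trial start. From the latest start (20 April 2022) to 1 July 2023 is 437 days; from the earliest start (14 February 2022) to 31 August 2023 is 563 days. The covariate period thus ends 437 to 563 days before the entry condition begins. It may reduce selection by care-seeking, but it does not make the subset equivalent to the full cohort.

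**3. What the planned comparison measures.** Let D(population, records) be the VAI minus usual care difference. Then

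D(subset, all) − D(full, VA) = [D(subset, VA) − D(full, VA)] + [D(subset, all) − D(subset, VA)].

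The first bracket is the population change and the second is the effect of the added records. The plan produces the left side only, because D(subset, VA) is not specified.

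**4. Illustration with assumed values.** Assume that half of each arm is in the subset, that VA captures a fraction c of doses equally in both arms, and that the combined records are complete. With usual-care uptake u and true effect e, the VA-only effect is c(u + e) − cu = ce, so u drops out. Effects are in percentage points.

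| Case | True effect in / outside subset | c | D(full, VA) | D(subset, VA) | D(subset, all) | Population part | Records part |
|---|---|---|---|---|---|---|---|
| A | 6 / 2 | 1 | 0.5×6 + 0.5×2 = 4.0 | 6.0 | 6.0 | +2.0 | 0.0 |
| B | 6 / 6 | 2/3 | (2/3)×6 = 4.0 | 4.0 | 6.0 | 0.0 | +2.0 |
| C | 3 / 5.57 | 0.7 | 0.7×(0.5×3 + 0.5×5.57) = 3.0 | 2.1 | 3.0 | −0.9 | +0.9 |

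A and B give the same two planned estimates, 4.0 and 6.0, for opposite reasons. C shows no shift although both parts are non-zero. The result does not depend on the 50% share. With shares of 30% to 70%, case A still gives 4.0 and 6.0 if the effect outside the subset is (4 − 0.3×6)/0.7 = 3.1 to (4 − 0.7×6)/0.3 = −0.7; case B does not involve the share. The subset VA-only column separates the cases every time.

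**5. Secondary outcome.** Under 9.1.5.1 the added records also decide who had not initiated or completed the series at randomization. Three things then change: the population, baseline status and the outcome. Repeating the model in the subset without stating whose records define the at-risk set would still mix the last two.

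**The case against.** The restriction is reasoned. Adding Gateway records for everyone would create the differential capture that SAP 9.1.3 sets out to avoid. This stands: the point is not to drop the subset but to give it a matching comparator. Flagged Gateway records make that run feasible; they do not specify it.

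The Bayesian analysis in SAP 9.1.4.2 also answers part of the question. For the primary outcome it holds the population fixed and varies ascertainment alone, with a lower bound taken from Medicare data. That is a real strength. But it works by imputation under partly investigator-set distributions, does not use Gateway records, and does not supply the VA-only estimate in the subset.

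The wording is softer than a strict restriction (a focus on these Veterans), and SAP 9.1.3 promises all-source sensitivity analyses without naming a population. A full-cohort run is therefore possible, but it is not specified.

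A reader might infer that 9.1.4.1 is the only analysis containing doses given outside VA. Protocol 5.8.a does not support that: VA data already include community immunizations reimbursed by VHA.

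A reader might also infer from the visit counts in Protocol 5.2.b that the subset result is biased in a known direction. Those figures are from June 2021, are not by arm, and come with the protocol's own warning that recorded unvaccinated status is unreliable. If return for care depended on vaccination status alone, and equally in both arms, the odds of vaccination in each arm would be multiplied by the same factor and the crude odds ratio would not change. A difference in proportions could still move. The visit counts are background only.

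**Conclusion.** The concern holds as a gap in specification. As written, the analysis cannot do what it is stated to do, because the plan yields only the sum of a population change and a records change. The decomposition needs no numerical assumption. The 73 to 199 days rest on activation falling within July and August 2023 at each site. The percentage-point cases are assumed and show only that the ambiguity is possible.

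The size and direction of any distortion cannot be computed: subset size, return rates by arm and capture rates are not in the documents. The primary analysis, with all eligible Veterans and VA records only, is not affected, and nothing here says that its estimate is wrong. A reader might also infer that one site is left out of the sensitivity analysis. The documents do not say so; they only give site coverage in two ways that need to be reconciled. The change should be made because this is where readers will look for the effect of external records, and it costs little.

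**What to change.** **Primary outcome (SAP 9.1.4.1 and Protocol 5.9).** In the same Gateway-era subset, run the 9.1.4 model once with VA-only outcomes and once with supplemented outcomes, with identical covariates. Base any statement about external records on that paired contrast, and limit it to Veterans who returned for care. Describe the subset VA-only result against the primary estimate as the combined effect of changing the population (selection, any difference in VA capture, any site not included), not as pure selection.

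**Secondary outcome (SAP 9.1.5.1 and Protocol 5.9).** State the at-risk set. Run the pair with that set held fixed, for example Veterans who had not initiated or completed the series at randomization according to all sources. Report separately the effect of reclassifying baseline status with the added records.

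**Reporting.** Give the number and proportion included by arm and by site, with each site's Gateway activation date. Reconcile the two statements on site coverage in 9.1.3 and 9.1.4.1, and state how the tenth site is handled.

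**Cost.** One or two extra runs per outcome, a table, and matching wording in both documents. The paired contrast will not generalize to Veterans who did not return for care. SAP section 9 allows changes up to final data lock and before unblinding; if that point has passed, label the added runs post hoc.
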